6.3 Conventions

6.3.1 Medical Coding

Adverse events and medical history will be coded using the Medical Dictionary of Regulated Activities (MedDRA) Version 24.1 (or higher). Conditions will be assigned to a System organ class (SOC) and preferred term (PT) based on the Investigator-reported verbatim term.

Any medications taken (other than study drug) will be coded using the World Health Organization Drug Dictionary (WHO Drug) September 2021 Version (or higher). Medications (both prior and

QMD Ref: Worldwide-TMP-ST-005-7.0 Effective: 12Aug2019	Governing QMD: Worldwide-SOP-ST-001
Confidentiality	y Statement
This document is the property of Worldwide Clinical Trials Inc. and may no prior approval from Worldwide Quality Assurance or in compl	
REF: Worldwide-TMP-QA-001f-1.3	Page 20 of 49

Worldwide Clinical Trials Controlled Quality Management Document		
WORLDWIDE CLINICAL TRIALS	Sponsor:	Integrative Research Laboratories Sweden AB
	Protocol Number:	IRL790C005
STATISTICAL ANALYSIS PLAN. PHASE 2-3-4		

concomitant) will be assigned to an Anatomical Therapeutic Chemical (ATC) Level 4 drug classification and Preferred Name based on the medication name reported on the eCRF.

6.3.2 Data Handling

All clinical data programming will be performed using SAS[®] statistical software package (Statistical Analysis System, Version 9.4 or higher)¹ and based on Clinical Data Interchange Standards Consortium (CDISC) data standards.

6.3.3 Validation Methods

All programming of datasets and outputs will be validated by fully independent double programming of values and manual review of format compared to the SAP and agreed shell template. Figures will be validated by manual review of format and visual inspection of graphical display compared to tabulated data. Independent programming (IP) by a Statistician (Stat IP) will be performed for all statistical analyses.

6.3.4 Summary Statistics

Continuous variables will be summarized by the number of non-missing observations, mean, median, standard deviation, and minimum and maximum.

Plasma concentration data will be summarized by number of non-missing observations (n), number of observations with concentrations below the limit of quantification (BLQ), arithmetic mean (mean), geometric mean, standard deviation (SD), median, minimum (min), maximum (max), and coefficient of variation (CV%). Concentrations that are BLQ will be set to zero for summary statistics. BLQ concentrations will be retained as BLQ in listings.

Categorical variables will be summarized by presenting the frequency and percent. Percentages will be based on the number of non-missing observations or the patient population unless otherwise specified. For each variable, all categories will be shown, including a category for missing where appropriate. Zero frequencies (but not the percent) within a category will be presented.

Incidences of adverse events, medical history and concomitant medications will be reported at the patient level. Patients can only be counted once within each PT and SOC under the highest severity and most related. Percentages will be calculated using the number of patients in the treatment group for the SAS. AE and medical history event tabulations will be presented by SOC and PT in

QMD Ref: Worldwide-TMP-ST-005-7.0 Effective: 12Aug2019	Governing QMD: Worldwide-SOP-ST-001	
Confidentiality	y Statement	
This document is the property of Worldwide Clinical Trials Inc. and may not be duplicated, copied, altered or removed from company without prior approval from Worldwide Quality Assurance or in compliance with Worldwide Standard Operating Procedures.		
REF: Worldwide-TMP-QA-001f-1.3	Page 21 of 49	

Worldwide Clinical Trials Controlled Quality Management Document		
WORLDWIDE CLINICAL TRIALS	Sponsor:	Integrative Research Laboratories Sweden AB
	Protocol Number:	IRL790C005
STATISTICAL ANALYSIS PLAN. PHASE 2-3-4		

descending overall frequency of incidence and then alphabetically for ties. Medications will be tabulated by ATC level 4 and preferred name in alphabetical order.

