14.8. Pharmacokinetic endpoints

PK variables measured in plasma include: mesdopetam parent drug and two of its metabolites, IRL902 (N-dealkylated) and IRL872 (acetylated).

Samples obtained pre-dose and 2 hour post dose (as an estimate of C_{max}) on Day 56 and Day 84 will be summarized by timepoint, visit, and mesdopetam dose level using descriptive statistics: number (n), arithmetic mean, standard deviation, minimum, median, maximum, geometric mean, and coefficient of variation (CV%).

If appropriate, the PK relationship between the treatment doses and plasma exposure (based on trough concentrations and C_{max}) of mesdopetam and its metabolites will be assessed using a power model.

Details of the PK analysis will be included in the SAP.

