3.7 Pharmacokinetic Endpoints

• Plasma concentrations of mesdopetam and its two main metabolites at pre-dose and 2 hours post-dose at 8 and 12 weeks of treatment.

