6.16 Pharmacokinetic Analyses

Plasma concentrations of mesdopetam and its two main metabolites (IRL902 [N-dealkylated] and IRL872 [acetylated]) will be obtained pre-dose and 2 hours post-dose (as an estimate of C_{max}) at Visit 4 (Week 8) and Visit 5 (Week 12).

QMD Ref: Worldwide-TMP-ST-005-7.0 Effective: 12Aug2019	Governing QMD: Worldwide-SOP-ST-001	
Confidentiality Statement		
This document is the property of Worldwide Clinical Trials Inc. and may not be duplicated, copied, altered or removed from company without prior approval from Worldwide Quality Assurance or in compliance with Worldwide Standard Operating Procedures.		
REF: Worldwide-TMP-QA-001f-1.3 Page 2		

Worldwide Clinical Trials Controlled Quality Management Document		
WORLDWIDE CLINICAL TRIALS	Sponsor:	Integrative Research Laboratories Sweden AB
	Protocol Number:	IRL790C005
STATISTICAL ANALYSIS PLAN. PHASE 2-3-4		

Concentration data will be summarized by analyte, adjusted dose level, and visit at each scheduled sample time (nominal time) for the PK analysis set, using descriptive statistics. Line plots will also be provided showing mean (SD) by dose level and visit for each analyte.

In addition, concentration data will be summarized by genotype (poor, intermediate, normal, and ultrarapid metabolizer), adjusted dose level, and visit at each scheduled sample time (nominal time) using descriptive statistics and line plots for the CYP Genotype Subset.

All concentration data will be listed.

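### Setting BLQ concentrations to zero for every summary statistic leaves the geometric mean zero or not calculable in any PK summary cell that contains a BLQ value

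*SAP*

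**What the plan says.** SAP 6.3.4 (Summary Statistics) asks for n, the number of BLQ observations, and then "arithmetic mean (mean), geometric mean, standard deviation (SD), median, minimum (min), maximum (max), and coefficient of variation (CV" as a percentage) for plasma concentrations. The next sentence sets the substitution: "Concentrations that are BLQ will be set to zero for summary statistics". The only exception follows directly: "BLQ concentrations will be retained as BLQ in listings".

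The other sections that bear on this do not change the rule:

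- SAP 6.16 (Pharmacokinetic Analyses) defines the tables: "Concentration data will be summarized by analyte, adjusted dose level, and visit at each scheduled sample time (nominal time) for the PK analysis set". It adds a display by CYP2D6 genotype for a subset. It refers only to descriptive statistics and has no BLQ rule of its own.
- Protocol 14.8 also requires the geometric mean ("number (n), arithmetic mean, standard deviation, minimum, median, maximum, geometric mean, and coefficient of variation (CV" as a percentage), gives no BLQ rule, and leaves PK details to the SAP.
- SAP 6.2.7 (Inexact Values) takes any value recorded as < x to be x for analysis. It neither exempts PK concentrations nor mentions 6.3.4.

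The endpoint served by these tables is in SAP 3.7: "Plasma concentrations of mesdopetam and its two main metabolites at pre-dose and 2 hours post-dose", at Weeks 8 and 12. Evaluating trough and 2-hour concentrations is a secondary objective (SAP 2.2, Protocol 5.2).

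**The concern.** Two adjacent sentences of SAP 6.3.4 cannot both be followed usefully once a BLQ value appears. The plan asks for a geometric mean and prescribes an input for which that statistic is either zero or undefined. A table cell would then show a geometric mean of 0 beside an arithmetic mean and median that look normal, or it would show no value.

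A program that turns the log of zero into a missing value would give a third result: a geometric mean over the quantifiable values only, on a row whose n and arithmetic mean still count the zero. That can be a reasonable statistic, but it is not the one the SAP describes.

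SAP 6.2.7 adds an ambiguity. If the laboratory reports BLQ results as < LLOQ, the SAP offers two substitutions for the same value, LLOQ and 0, without saying which takes precedence.

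At stake is the readability of the PK tables. No efficacy or safety conclusion is involved.

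**Working it through.** The documents state no figure on this point, so there is none to reproduce. The check is algebraic, with an illustration.

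**Number of cells.** SAP 6.16 gives 3 analytes × 3 active doses × 2 visits × 2 sample times = 36 cells, before the genotype display. Protocol 9.4 says that only active-group samples are assayed, so zeros from placebo patients are not the source of the problem.

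**Algebra.** GM = (x₁·x₂·…·xₙ)^(1/n) = exp(mean of ln xᵢ). If one xᵢ = 0, the product is 0 and so GM = 0. In the log form ln 0 = −∞, so the mean of the logs does not exist. Neither result depends on n or on the other values.

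**Illustration.** Take n = 31, the evaluable number per group that SAP section 4 assumes for the primary endpoint (the PK n is not given). Use lognormal quantiles with true GM 100 and an assumed CV: xᵢ = 100·exp(s·qᵢ), with s = √ln(1 + CV²) and qᵢ the standard normal quantile at (i − 0.5)/31. Make the lowest value BLQ.

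| | CV 30% | CV 50% | CV 80% |
|---|---|---|---|
| Lowest value before substitution | 53.3 | 36.4 | 22.2 |
| GM as the SAP is written | 0 or none | 0 or none | 0 or none |
| Arithmetic mean, before → after the zero | 104.2 → 102.5 | 111.2 → 110.1 | 126.4 → 125.6 |
| Median, before → after | 100 → 100 | 100 → 100 | 100 → 100 |
| GM, quantifiable values only (n = 30) | 102.1 | 103.4 | 105.1 |
| GM, BLQ = LLOQ/2, assumed LLOQ 1 to 20 | 86.0 to 94.7 | 87.1 to 95.9 | 88.5 to 97.5 |

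The last two rows can be checked by hand. Dropping the lowest value gives 100·(100/lowest)^(1/30); at CV 30%, (100/53.3)^(1/30) = 1.021. Substituting gives 100·((LLOQ/2)/lowest)^(1/31); at CV 30% and LLOQ 20, (10/53.3)^(1/31) = 0.947.

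**Conflict with SAP 6.2.7.** At CV 50% and an assumed LLOQ of 10, a result recorded as < 10 becomes 10 under 6.2.7. The GM is then 100·(10/36.4)^(1/31) = 95.9. Under 6.3.4 the same sample gives 0 or no value.

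**Chance that a cell is affected.** P(at least one BLQ among 31) = 1 − (1 − p)³¹, where p is the probability that a single sample is BLQ, taking samples as independent. The documents do not give p, so the range below is assumed.

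| p | 0.5% | 1% | 2% | 5% | 10% |
|---|---|---|---|---|---|
| Chance per cell | 14% | 27% | 47% | 80% | 96% |

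If no sample is BLQ, the rule does no harm.

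**The case against.** The strongest reply is that the consequence is small and partly visible already. SAP 6.3.4 reports the number of BLQ observations, so a reader can see which cells are affected. The arithmetic mean, median and range remain usable, and listings keep BLQ as BLQ. SAP 6.16 plots the mean with SD, and no PK inference rests on the geometric mean. Independent double programming (SAP 6.3.3) would probably bring a zero-versus-dropped discrepancy to light. All of this stands, and it is why the priority is low. It does not rescue the rule: double programming checks against the SAP, and the SAP prescribes the zero.

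A reader might also infer four stronger points that the documents do not support:

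- **That BLQ troughs are likely, especially at 2.5 mg.** With a half-life of about 7 h (Protocol 4.6) and doses about 8 h apart (Protocol 9.2), the morning trough falls about 16 h after the previous dose, and 0.5^(16/7) = 0.21. That is only a ratio. Without an LLOQ or expected concentrations it says nothing about BLQ frequency. The half-life is given for the parent drug only.
- **That exposure by CYP2D6 genotype is part of the secondary objective.** The objective names trough and 2-hour concentrations. The genotype summary is an additional display in patients who consented to optional testing.
- **That leaving out BLQ values is wrong in itself.** A geometric mean of quantifiable values is legitimate if it is stated and its n is shown.
- **That LLOQ/2 is the right substitute.** In the illustration, the quantifiable-only result is closer to 100 than LLOQ/2 at every LLOQ tried for CV 30% and 50%; at CV 80% the order depends on the LLOQ. All the assumed LLOQs lie below the lowest model value, so the example represents a stray low sample and does not settle the choice.

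**Conclusion.** The point holds as a defect in a stated rule. Followed literally, SAP 6.3.4 gives a geometric mean of zero, or none, in every PK summary cell with at least one BLQ value. No other section of the SAP or protocol exempts the geometric mean. This conclusion rests on algebra alone and does not depend on the assumed CVs or LLOQs.

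Its reach is limited to the descriptive trough and 2-hour tables and the genotype display, and it arises only if BLQ values occur. Up to 36 main cells are exposed; how many would be affected cannot be estimated from the documents. The primary and key secondary analyses are untouched. It is a low-priority correction, worth making before unblinding so that the convention is not chosen after the concentrations have been seen.

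**What to change.** In SAP 6.3.4:

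1. Limit the zero substitution to the arithmetic statistics.
2. Add one sentence with a separate rule for the geometric mean. Either calculate it from quantifiable values only and show their n beside the BLQ count, or use a stated substitution such as LLOQ/2. If the planned CV% is meant as a geometric CV, apply the same rule to it.
3. State that 6.3.4 overrides 6.2.7 for PK concentrations.

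If the optional power model of Protocol 14.8, which the SAP does not carry forward, is ever fitted on the log scale, it will need a stated BLQ rule as well.

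The cost is two or three sentences and a minor programming note. The downside is a bias in the geometric mean of cells with BLQ values: upward if they are left out (2% to 5% in the illustration), and downward there with LLOQ/2 (2.5% to 14%, depending on the assumed LLOQ and CV).

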6.3.5 Decimal Places

Decimal places for derived data described in Section 6.2 will be determined by the scale of measurement unless otherwise stated. No decimal places will be displayed if the smallest calculated value is \geq 100; 1 decimal place will be displayed when the smallest value is within the interval (10, 100), with 10 being inclusive; 2 decimal places will be displayed when the smallest value is within (1, 10), with 1 being inclusive; and so on for even smaller scales of measurement. Two decimal places will be displayed for the calculation of average daily hours in each motor state.

For summary statistics, n will be reported as a whole number. Means, medians, and percentiles will be displayed to one more decimal place than the data, dispersion statistics (e.g., standard deviation) will have two more decimal places, and the minimum and maximum will be displayed to the same number of decimal places as reported in the raw data. Percentages will be displayed with one decimal place. P-values will be quoted to 3 decimal places. P-values < 0.001 will be presented as p<0.001 unless otherwise specified. Plasma concentration data will be reported to 3 significant figures.

All data presented in the individual patient listings will be as recorded on the eCRF.

6.3.6 Data Displays

All observed data and change from baseline to scheduled post-baseline visits will be summarized unless otherwise specified. All collected data will be listed.

All clinical data tabulations, figures and listings will be generated as individual Rich Text Format (.rtf) files using $SAS^{\mbox{\tiny (SAS)}}$ (Version 9.4 or higher)¹. Data summaries and graphical analyses will be reported within Section 14 of the CSR and individual patient data listings within Appendix 16.2 of the CSR.

Patient disposition, baseline characteristics, demographic, compliance, concomitant medication, and adverse event data will be presented by treatment group and overall. All other data will be presented by treatment group only.

Treatment group labels will be displayed as follows:

Worl	dwide Clinical T	rials Controlled Qu	ality Management	Document
WORLDWIDE CLINICAL TRIALS		Sponsor:	Integrative Resear	ch Laboratories Sweden AB
CLIN	NICAL TRIALS	Protocol Number:	IRL790C005	
STATISTICAL ANALYSIS PLAN. PHASE 2-3-4				
Mesdopetam	Mesdopetam	Mesdopetam	All	Placebo

7.5 mg b.i.d.

(N=XX)

Mesdopetam

(N=XX)

b.i.d.

(N=XX)

Listings will be sorted in the following order: treatment group, patient, visit, and parameter, unless otherwise stated. All collected data will be listed.

6.4 Patient Disposition

2.5 mg b.i.d.

(N=XX)

Patient disposition will be summarized by randomized treatment group and overall, as follows:

- The number of patients entering the study.
- The number of patients completing the study

5 mg b.i.d.

(N=XX)

- The number of patients with early termination and the reasons for early termination.
- The number of patients who were screened, who were re-screened, and who failed screening, with the reason for screen failure (for re-screened patients, the most recent reason for screen failure will be taken).
- The number of patients in each analysis set. •
- The number of patients excluded from the PPS and the reason for exclusion.
- The number of patients in each analysis set by country.
- The number of patients attending each visit.
- The number of patients with missed or remote visits due to COVID-19. •

By-patient listings of all disposition data will be presented for all enrolled patients as follows:

- Study completion or early termination and reason for early termination.
- Randomization details including randomization stratum.
- Screening, re-screening and reason for screen failure.
- Inclusion in analysis sets.
- Missed or remote visits due to COVID-19. •

6.5 **Protocol Deviations**

All reported protocol deviations (PDev) will be summarized by treatment group, PDev category and PDev classification (Major and Minor). PDevs related to COVID-19 will also be summarized

QMD Ref: Worldwide-TMP-ST-005-7.0 Effective: 12Aug2019	Governing QMD: Worldwide-SOP-ST-001
Confidentiality	y Statement
This document is the property of Worldwide Clinical Trials Inc. and may not be duplicated, copied, altered or removed from company without prior approval from Worldwide Quality Assurance or in compliance with Worldwide Standard Operating Procedures.	
REF Worldwide-TMP-OA-001f-1 3	Page 23 of 49

Worldwide Clinical Trials Controlled Quality Management Document		
WORLDWIDE CLINICAL TRIALS	Sponsor:	Integrative Research Laboratories Sweden AB
	Protocol Number:	IRL790C005
STATISTICAL ANALYSIS PLAN. PHASE 2-3-4		

separately. All reported PDevs will be listed, and a separate listing of PDevs related to COVID-19 will be provided.

6.6 **Baseline Comparability**

Comparability of treatment groups with respect to patient demographics and baseline characteristics will be assessed in a descriptive manner.

Demographic and baseline characteristic summaries will be presented by treatment group and overall, based on the randomized treatment group for the FAS and the SAS. If these sets are equal, only the FAS will be presented. All collected data will be listed. Summaries will be presented for the following variables:

Demographic Data

- Age at Screening (years)
- Age by category (< 65 years and \geq 65 years)
- Gender
- Fertility status (female only)
- Ethnicity
- Race (where more than one race is selected the patient will be presented under the 'Multiple races' category in the summary but each selected race will be identified in the listing).

Baseline Characteristics

- Weight at Screening (kg)
- Height at Screening (cm)
- BMI at Screening (kg/m²)

Clinical Characteristics

- Hoehn and Yahr Scale
- Years from PD diagnosis at baseline and will be calculated as follows: Years from PD Diagnosis at Baseline = (Day 1 - Start Date of PD from the medical history) / 365.25. If the start date of PD is partial, then only year portion will be used for calculation and will follow Section 6.3.5 for rounding of decimals
- Average levodopa dose based on evaluable reported usage (in mg) taken on or after first dose of study drug

QMD Ref: Worldwide-TMP-ST-005-7.0 Effective: 12Aug2019	Governing QMD: Worldwide-SOP-ST-001
Confidentiality	y Statement
This document is the property of Worldwide Clinical Trials Inc. and may not be duplicated, copied, altered or removed from company without	
prior approval from Worldwide Quality Assurance or in compliance with Worldwide Standard Operating Procedures.	
REF: Worldwide-TMP-OA-001f-1 3	Page $24 \text{ of } 49$

- ON-time (hours) with troublesome dyskinesia
- Randomisation strata (<6 hours or \geq 6 hours of ON-time with troublesome dyskinesia)
- MDS-UPDRS question 4.2 score (functional impact of dyskinesias)
- MMSE at Baseline
- Physical examination by body system at baseline

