¹² Three 24-hour home diaries to be completed during separate days during the week (can be three consecutive days or any combination of days during the week) prior V1, V3, V4 and V5 (i.e. in total 12 diaries during the study). Set dates for the patient complete diaries to be agreed in advance. Clinic to call the patient the working day before the first 24-hour diary completion period, as a reminder, and the working day after the last 24-hour diary completion period to encourage compliance.
¹³ First dose to be taken in the evening at day 1
¹⁴ Taken within 15 min pre-dose and approx. 2 hours (± 15 min) after morning dose of IMP
¹⁵ Only collect the bottle if dose is reduced

CONTACT NAME AND ADDRESS

Sponsor:	Integrative Research Laboratories Sweden AB (IRLAB)
Address:	Integrative Research Laboratories Sweden AB (IRLAB) [name],
Contact details:	Sweden [contact] E-mail: [contact]
Personnel:	[name], PhD, Chief Medical Officer (CMO)

Confidential	Version: 5.0	Page 17 of 74
Protocol: IRL790C005	Date: 5 Mar 2021	

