7. PATIENT SELECTION CRITERIA

7.1.Patient recruitment

Patients will be recruited from the population of outpatients at the study sites. Patients may also be recruited by other methods such as clinic lists, research registers, and patients learning about the study from websites or other sources or from a local research event. Potentially eligible patients interested in taking part of the study may therefore be referred from other sites.

The Investigator will keep records of all patients screened and included. The reason for screen failure should be stated for all patients screened but not included. The reason for early termination/withdrawal should be stated for all patients included but not completed.

140 randomized patients are required for this study.

Confidential	Version: 5.0	Page 33 of 74
Protocol: IRL790C005	Date: 5 Mar 2021	e

7.2.Inclusion criteria

For inclusion in the study, patients must fulfil all the following criteria:

- 1. Male or female \geq 30 and \leq 79 years of age at the time of screening.
- 2. Signed a current Ethics Committee approved informed consent form.
- 3. PD, per UK Parkinson's Disease Society (UKPDS) Brain Bank Clinical Diagnostic Criteria.
- 4. Minimal amount of 2 hours of levodopa-induced daily "ON-time with troublesome dyskinesia" during waking hours.
- 5. Functional impact of dyskinesias determined as a score of ≥2 as per Question 4.2 of the MDS- UPDRS.
- 6. On a stable regimen of antiparkinson medications for at least 30 days prior to first home diary completion, which must include a levodopa preparation administered 3-8 times/day (excluding nighttime levodopa) and willing to continue the same doses and regimens during study participation. Rescue medications such as Madopar dispersable and Apomorphine injections are allowed if prescribed PRN prior to study entry.
- 7. Any other current and allowed prescription/non-prescription medications and/or nutritional supplements taken regularly must have been at a stable dose and regimen for at least 30 days prior to first home diary completion and the patient must be willing to continue the same doses and regimens during study participation (this criterion does not apply to medications that are being taken pre-study only on an as-needed basis).
- 8. Able to complete 24-hour patient home diaries of which two valid diaries must be presented at Visit 1.

7.3.Exclusion criteria

Patients must not enter the study if any of the following exclusion criteria are fulfilled:

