14.4. Study population

All basic information regarding the sample of patients recruited to represent the PD population with dyskinesia will be summarized. This will include all assessments performed prior to the start of treatment (screening) including demographics (gender, age, ethnicity and race), medical history (including smoking), diagnosis of PD, duration of PD, height, weight, BMI, MMSE, Hoehn and Yahn Scale score and prior medications. Each will be described overall and according to treatment group.

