6.2.2 Baseline

Baseline is defined as the last non-missing value (either scheduled, unscheduled or repeat) before the patient receives the first dose of study drug.

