6.8 Medical History

Separate tabulations of prior and ongoing conditions at screening will be presented by treatment group and overall, for the SAS. Prior conditions are those with a stop date prior to screening and conditions are ongoing otherwise. Tabulations will be presented by SOC and PT in descending frequency of incidence in the pooled mesdopetam arm and then alphabetically for ties. All reported medical history will be listed.

6.9 **Prior and Concomitant Medications**

Prior medications are defined as any medications starting and stopping prior to date of first dose of study drug. Concomitant medications are defined as medications taken on or after the date of first dose of study drug.

Prior and concomitant medications will be presented alphabetically by ATC Level 2 classification followed by ATC level 4 classification and Preferred Name for each treatment group in the SAS.

A separate tabulation will also be provided for all medications reported under ATC Level 1 = Nervous System, Level 2 = Anti-Parkinson Drugs. Medications will be presented by ATC Level 3 and Preferred Name by treatment group and overall.

QMD Ref: Worldwide-TMP-ST-005-7.0 Effective: 12Aug2019	Governing QMD: Worldwide-SOP-ST-001
Confidentiality Statement	
This document is the property of Worldwide Clinical Trials Inc. and may not be duplicated, copied, altered or removed from company without prior approval from Worldwide Quality Assurance or in compliance with Worldwide Standard Operating Procedures.	
REF: Worldwide-TMP-OA-001f-1.3	Page $25 \text{ of } 49$

Worldwide Clinical Trials Controlled Quality Management Document		
WORLDWIDE CLINICAL TRIALS	Sponsor:	Integrative Research Laboratories Sweden AB
	Protocol Number:	IRL790C005
STATISTICAL ANALYSIS PLAN. PHASE 2-3-4		

Average levodopa dose will also be obtained from the medication log. The first reported levodopa dose taken on or after first dose of study drug will be summarized per treatment group alongside clinical characteristics.

All reported medications will be listed. Medication logs will also be reviewed by the Sponsor and any non-permitted medications will be identified and listed separately.

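### The levodopa row in the SAP's baseline comparability table uses post-randomisation data and is worded in two ways, so it may misstate baseline balance; the effect is confined to a descriptive table and is probably small

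*SAP*

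**What the plan says.** SAP 6.6 (Baseline Comparability) sets the purpose of the table: "Comparability of treatment groups with respect to patient demographics and baseline characteristics will be assessed in a descriptive manner". Under Clinical Characteristics it lists "Average levodopa dose based on evaluable reported usage (in mg) taken on or after first dose" of study drug.

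SAP 6.9 (Prior and Concomitant Medications) says that an average levodopa dose will come from the medication log, and continues: "The first reported levodopa dose taken on or after first dose of study drug will be summarized per treatment group alongside clinical characteristics".

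SAP 6.2.2 fixes the general rule: "Baseline is defined as the last non-missing value (either scheduled, unscheduled or repeat) before the patient receives the first dose of study drug". Protocol 14.1 defines baseline in the same sense. Protocol 14.4 describes the study-population summary as covering assessments made before treatment begins.

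On background therapy, inclusion criterion 6 (Protocol 7.2) requires at least 30 days of stable antiparkinsonian medication before the first home diary. It also requires levodopa 3 to 8 times a day and a patient "willing to continue the same doses and regimens during study participation". Protocol 8.2 has all therapy recorded on the CRF from four weeks before the screening period.

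**The concern.** A baseline table should hold only quantities that treatment cannot have altered. This row is built from use after study drug has started, so it could carry an effect of treatment.

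Levodopa is also the row that a reader of this trial is likely to look for, because the condition studied is levodopa-induced dyskinesia. There is a reason why post-dose changes might differ by arm. Parkinsonism was the most common adverse event in Phase 2a (Protocol 4.6) and is listed as a potential event in Protocol Table 4. If levodopa use moved in response, the row could show an imbalance that did not exist at randomisation, or mask one that did.

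The two wordings add a practical problem. SAP 6.3.3 requires independent double programming, and two programmers could each follow the text and produce different numbers.

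**Working it through.** The plan states no levodopa figure, so there is none to reproduce. The check has three parts.

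**1. Timing.** Randomisation is at Visit 1 on Day 1. For the first IMP dose, the schedule footnote says: "First dose to be taken in the evening at day 1". Any levodopa use counted from that dose onward is therefore post-randomisation.

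| Source | What it covers | Relation to first dose |
|---|---|---|
| SAP 6.2.2, Protocol 14.1 | Baseline | Before |
| Protocol 14.4 | Study-population summary | Before |
| SAP 6.6 | Average reported levodopa usage, no end date | From first dose onward |
| SAP 6.9 | First reported levodopa dose | From first dose onward |

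SAP 9, which lists changes to the protocol analysis, does not mention this row.

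**2. Whether another summary supplies the pre-dose figure.** SAP 6.9 counts a medication as prior only if it both started and stopped before first dose, so ongoing levodopa falls under concomitant. The anti-Parkinson tabulation is by ATC level 3 and preferred name, not by dose. Only the listings would show a pre-dose levodopa dose.

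**3. Size of the timing error under the average definition.** These are assumptions, not document figures: a share p of an arm changes levodopa by 25% in the same direction after d days, usage is averaged over the 84 treatment days, and patients who change have the same mean starting dose as the rest of the arm.

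Relative shift of arm mean = p × 25% × (84 − d)/84

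| p | d = 9 | d = 28 | d = 56 |
|---|---|---|---|
| 0% | 0% | 0% | 0% |
| 5% | 1.1% | 0.8% | 0.4% |
| 10% | 2.2% | 1.7% | 0.8% |
| 20% | 4.5% | 3.3% | 1.7% |

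For example, with p = 20% and d = 9: 0.20 × 0.25 × 75/84 = 4.5%. With p = 5% and d = 56: 0.05 × 0.25 × 28/84 = 0.4%. If only one arm changes, the shift is also the spurious between-arm difference.

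Under the first-reported-dose definition the timing shift is zero, unless the change comes at or before that first record.

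**Consequence for the primary analysis.** The model in SAP 6.12.3 contains treatment, visit, country, treatment by visit, baseline good ON-time and the stratification factor. Levodopa dose is not among them. The stated 92% power uses a 3-hour difference, SD 3.5 and 31 evaluable patients per group: 3/(3.5 × √(2/31)) = 3.37, and 3.37 − 1.96 = 1.41, which gives 92.1% by normal approximation. None of these inputs involves levodopa dose.

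**The case against.** The strongest reply is that the wording is clumsy but harmless. Because SAP 6.9 classes ongoing drugs as concomitant, the timing phrase may be meant only to select the current regimen over stopped entries. SAP 6.9 may also be specifying SAP 6.6: the first dose per patient, averaged within each arm. With a stable regimen required, the first record after the Day 1 evening dose would normally be the pre-study regimen.

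Much of this stands. It makes a large error unlikely, and it means that an outright contradiction between 6.6 and 6.9 is not proved. But the SAP states neither reading. Willingness to keep the same doses does not guarantee that they are kept, and Protocol Table 3 itself asks for adherence to antiparkinsonian medication to be reviewed at Visit 3.

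Three stronger inferences are tempting, and the documents do not support them:

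- **That the table cannot show whether background therapy was balanced.** Under a stable regimen the first post-dose record is a close proxy for baseline, and the average departs from it only as far as doses change.
- **That the plan removes any check on whether a gain in good ON-time came from different levodopa use.** Medications are collected at every contact and listed, anti-Parkinson drugs are tabulated by arm, and protocol deviations are summarised by arm. What is missing is a summary of dose. An on-treatment average would itself show something about use during treatment.
- **That the error is large because it can be large for one patient.** An assumed patient on 750 mg/day cut to 500 mg/day from Day 15 averages (14 × 750 + 70 × 500)/84 = 542 mg/day, 28% below baseline. That is one invented patient who departs from the required regimen, whereas the table compares arms.

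**Conclusion.** The row is wrong as written: a post-randomisation quantity is presented as a baseline characteristic, against SAP 6.2.2 and Protocol 14.4. SAP 6.6 and 6.9 word it differently, and neither gives an averaging window or says mg/day.

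The consequence is limited. The row may misstate baseline balance if levodopa changes after first dose. In the assumed scenarios the arm mean shifts by about 0.4% to 4.5% under the average definition and by about zero under the first-dose definition. Those figures rest on assumed shares, sizes and timings of dose change, because the documents give no rate of levodopa change. They also assume that log entries are read as daily totals. The documents do not show how the log records dose. The missing per-day unit needs settling even if no patient changes regimen, since levodopa is taken several times a day.

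This is a descriptive reporting defect. The primary estimate, alpha and power are not affected. It is worth correcting because the row bears directly on the condition studied and the correction is cheap.

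**What to change.** In SAP 6.6 and 6.9, replace both wordings with one definition: total scheduled daily levodopa dose, in mg/day, summed over all levodopa products, in effect at the last medication-log record before first dose of study drug. This agrees with SAP 6.2.2 and Protocol 14.4.

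Report on-treatment levodopa dose, or change from that baseline, in a separate table by arm, labelled post-baseline. No document promises this second table, but it keeps the on-treatment information that the present wording places in the baseline table.

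The cost is SAP wording and one descriptive table. Protocol 8.2 already requires the medication data, from four weeks before screening, to be on the CRF, so no new collection is needed.
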